#### **1** SUMMARY

This project will assess the relationships between neck strength and the incidence, severity, and duration of concussions in student athletes in order to evaluate the effectiveness of a neck strengthening training regime as a primary intervention for reducing the risk of sport-related concussion.

#### 2 BACKGROUND

Sport-related concussion is a common injury that results in more than 200,000 emergency department visits annually, 65% of which are children aged 5 to 18. Recognized as a major public health concern, sport-related concussion diagnoses in the United States have increased by 43% overall over the last 5 years. Rates of increase over the same time span were also found to be higher for pediatric (71%) and female (up to 118%) populations, consistent with research indicating that the incidence and clinical outcomes of concussion vary with sex and age; specifically, significantly higher risks and poorer outcomes have been reported for younger and female populations. Because the developing brains of children and adolescents are uniquely vulnerable to diffuse brain injury, single or repeated concussions have potential for severe acute and long-term complications in these young athletes.

Low neck strength is a risk factor thought to contribute to an elevated concussion risk. Previous studies have shown that athletes with smaller and weaker necks experience greater resultant linear and angular head displacements, velocities, and accelerations after impact. Because these parameters represent the primary mechanisms contributing to a concussive event, further studies clarifying the relationships between neck strength and the risk and clinical outcomes of concussion are warranted. To date, only 1 study has examined the relationship between neck strength and concussion incidence; in a prospective study of high school athletes, Collins et al measured isometric neck strength parameters using a hand-held tension scale and monitored the concussion rate over several sports sessions. Neck strength was found to be a significant predictor of concussion incidence among high school students, with concussed athletes demonstrating 11% to 22% reduction in neck strength compared with nonconcussed athletes.

Given the increases in the reported incidence of head injuries sustained by young student athletes in the United States, it is essential that high school and university athletics programs have access to inexpensive, effective, and easy-to-implement strategies for the prevention of concussions. Collectively, the results of previous studies suggest that interventions aimed at increasing athletes' neck strength may be effective for decreasing the risk and symptoms of concussion. Imperative to the development of such interventions are additional studies that quantify the extent to which the severity and duration of concussion symptoms are a function of neck strength.

#### **3** STUDY PURPOSE

The purpose of the project is to evaluate the effectiveness of neck strengthening as a primary prevention mechanism against concussion.

# 4 STUDY PROTOCOL

### 4.1 **OVERVIEW**

This project has the following goals:

- 1. Determine whether baseline measurements of neck strength correlate with the incidence, severity, and duration of concussion symptoms;
- 2. Determine whether a standardized neck strengthening training regime reduces the risk of concussion and the severity and duration of symptoms; and
- 3. Determine whether the relationships between neck strength and the clinical symptoms of concussion are independent of gender.

Subjects aged 5 to 22 who are involved in organized, academic or community-based contact/collision sports activities at Gustavus Adolphus College, member schools of the Independent Metro Athletic Conference (IMAC) conference, and The Sanneh Foundation participate in an instructor-led neck-strength training program. Subjects enrolled in the study will be followed for up to 3 years to assess whether the incidence, severity, and duration of concussion symptoms varies as a function of neck strength in young athletes. Anthropometric measurements, neck strength parameters, cognitive assessments, and an eye-tracking assessment will be performed for each subject at baseline, and at yearly intervals thereafter in the absence of a reported head injury. In addition, anthropometric and neck-strength measurements will be recorded at regular intervals during the study to quantify the effectiveness of the strength training regime. Subjects diagnosed with concussion during the study will be assessed for the severity and duration of postconcussion symptoms using eyetracking methodology and traditional cognitive assessments. Clinical outcomes will be assessed immediately following a concussive event and monitored by research staff until symptoms resolve. Data will be collected by onsite study volunteers trained by [name] or another member of the Brain Injury Research Lab staff at HCMC. All aspects of the study design will be overseen and approved by [name].

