# 4.2 STUDY DESIGN AND METHODS-BRIEF

STUDY TYPE	Multicenter, observational, open analytical study
SAMPLE SIZE	1500
Sites	Sports facilities onsite at Gustavus Adolphus, member schools of the IMAC conference, and The Sanneh Foundation.
STUDY DURATION	Approximately 3 years
Study Arm(s)	Single-arm design

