# Table 1: Study Design Summary

HSR# 17-4360

All subjects will undergo an instructor-led, standardized neckstrengthening training regime

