### Intervention

Subjects will be invited to participate in a twice-weekly, instructorled, neck-strengthening training program. In each training session, subjects will perform a variety of lightly-weighted and nonweighted resistance exercises.

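### The stated purpose and goal 2 promise the effect of training on concussion, but every subject trains and no planned analysis contrasts training with its absence

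*Protocol*

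**What the plan says.** **What is promised.** Protocol section 4.1, goal 2, is to "Determine whether a standardized neck strengthening training regime reduces the risk of concussion and the severity and duration of symptoms". The Summary (section 1) says that relationships between strength and concussion are studied "in order to evaluate the effectiveness of a neck strengthening training regime as a primary intervention for reducing the risk of sport-related concussion". Section 3 gives the whole purpose as to "evaluate the effectiveness of neck strengthening as a primary prevention mechanism against concussion". The second sentence of 4.3 adds an aim about whether the program lowers the duration and severity of symptoms; it does not mention incidence.

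**What is designed.** Section 4.2 describes a "Multicenter, observational, open analytical study" with a "Single-arm design", and Table 1 says "All subjects will undergo an instructor-led, standardized neckstrengthening training regime".

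**What is analysed.** Table 1 (Data analysis) and section 6.3 name two analyses. One is a repeated-measures ANOVA of neck strength, described as evaluating the effectiveness of the training program. The other is a set of logistic and linear regressions relating neck-strength parameters to concussion risk and functional outcomes. Adjustment for sex is stated. Sections 4.1 and 4.6 use the same language for the strength readings; in 4.1, "measurements will be recorded at regular intervals during the study to quantify the effectiveness of the strength training regime".

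**Who trains.** The Intervention row of Table 1 says "Subjects will be invited to participate in a twice-weekly" program. The design summary has everyone training. Footnote a ties training to the length of the sport program and to the athlete's regular training periods. Section 4.5.2 says that all subjects train twice weekly for as long as they are enrolled, and also expects duration to differ by sport and program.

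**The concern.** A claim that training reduces concussion compares the risk under training with the risk without it. The plan collects data on the first only. Followed exactly, it delivers a change in neck strength over time and an observational association between strength and concussion. Neither is an effect of training on concussion, and joining the two does not make one: strength may rise for reasons other than training, and stronger athletes may differ in age, size or sport.

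Two things are at stake. The stated purpose, goal 2 and the second aim would go unanswered. And an increase in strength that is likely in growing children could be reported, in the protocol's own words, as showing that the training is effective, and then read as support for a prevention claim in youth sport.

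**Working it through.** **1. The plan's own figure contains no training effect.** Inputs from 6.4: R = 0.25 between neck strength and reduction in severity, power 0.80, alpha 0.05 (taken as two-sided), incidence 11%, attrition 15-20%.

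- Fisher z: n = ((1.960 + 0.842)/atanh(0.25))² + 3 = (2.802/0.2554)² + 3 = 123.3, so 124 concussed subjects; 124/0.11 = 1127.3, so 1128.
- The stated 1198 is not reproduced exactly. It implies 1198 × 0.11 = 131.8, about 132 concussed subjects. The gap is small and plays no part in this point.
- Attrition: 1198/(1 − 0.20) = 1497.5, which agrees with the stated 1500.

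The calculation concerns strength against severity. It gives no comparator rate and no assumed effect of training, so there is no training figure to reproduce.

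**2. The concussion contrast.** Goal 2 needs risk(trained) − risk(untrained). Under 4.2, Table 1 and 4.5.2 all subjects train and none is untrained, so all of the roughly 132 expected concussed subjects are trained. The planned model has the form

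logit P(concussion) = b0 + b1 × strength + b2 × sex.

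A training indicator would equal 1 for every subject and could not be separated from b0. The coefficient b1 answers goal 1, not goal 2.

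**3. Substitutes within the protocol.**

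| Possible substitute | What the protocol gives |
|---|---|
| Historical rate | The 11% incidence (6.4) is unpublished, is used only for sample size and is not named as a comparator |
| Length of training | Varies by sport and program (footnote a; 4.5.2), so it is confounded with both; no stated analysis uses it |
| Declined or missed training | The invitation wording allows it, Table 1 and 4.5.2 do not, and no attendance analysis is stated |

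**4. The strength ANOVA.** With one trained group, the expected change between two readings is

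mean change = training + growth + sport conditioning + test practice.

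There is one estimable quantity and four terms. A sex main effect leaves the mean change as it is. A sex-by-time interaction gives one such sum for each sex and still does not split it.

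**5. Can growth be partly separated?** Yes, under an assumption. Baseline strength is measured at entry (4.8.1) in subjects aged 5 to 22. Let strength = a + b × baseline age + g × time. Since age at visit = baseline age + time, this equals a + b × (age at visit) + (g − b) × time. If there is only growth, and the age slope between subjects equals the slope within subjects, then g = b and the time term is zero.

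A simulation agrees: 400 subjects, two readings, growth only, an assumed slope of 3 units per year and three random seeds. The time effects were 2.71, 2.88 and 3.35 unadjusted, and −0.37, −0.01 and 0.35 (standard error about 0.38) with age at visit in the model. The slope is assumed, and the equality of the two slopes was built in.

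**The case against.** The strongest reply is that this is a study of neck strength. The primary objective (4.3), the primary hypothesis (4.4), goals 1 and 3 and the sample size (6.4) all concern strength, and training enters 4.3 only as something that the study also generally aims to examine. The design is openly labelled observational. Covariates for the ANOVA belong in a statistical analysis plan that is not shown. Much of this stands, and it limits the point.

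- A reader might infer that the whole study fails. The documents do not support that: the association of strength with concussion needs no untrained group.
- A reader might infer that growth cannot be separated from training at all. That is too strong. The baseline strength-by-age relation allows a partial separation, as shown above, though not for conditioning or practice.
- A reader might count the absence of age or body size from the stated adjustments as an error. Covariate choice can be left to the analysis plan, adjusting for weight could remove part of a real training effect, and the stated sex adjustment could mean an interaction.
- A reader might want a false-positive rate for the ANOVA. Any such figure depends on an assumed drift and an assumed number of repeat readings; the documents give neither.
- The passages on exposure are partly compatible: invitation fits voluntary participation, and footnote a and 4.5.2 both link training to the sport program. What remains is a need for clarification.

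The reply does not rescue goal 2. It is listed separately from goal 1, the Summary and Purpose are worded around the same promise, and no analysis plan can create an untrained comparison that the design excludes.

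**Conclusion.** The point holds. Sections 1 and 3, goal 2 in 4.1 and the second aim in 4.3 claim something that the design cannot deliver. The size is categorical, not numerical: no untrained subjects, no named comparator and no training term in any stated analysis. This rests only on the protocol's statements that the study has one arm and that all subjects train; it needs no assumed effect size or growth rate.

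On strength, the conclusion is narrower. The ANOVA validly tests whether mean strength changes over time. It does not by itself show that training caused the change, and describing it as effectiveness is wrong as written. How much of any change would be growth cannot be computed from the documents.

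Goals 1 and 3, the primary objective and the basis of the sample size are not affected.

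**What to change.** 1. Delete goal 2 (4.1) and the second aim (4.3), or restate both as: *describe change in neck strength during the neck-strengthening program*. Reword sections 1 and 3 as the prospective association of neck strength with the incidence, severity and duration of concussion in athletes taking part in the program. Add to 4.2: *The single-arm design does not estimate the effect of training on concussion.*

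2. In 4.1, Table 1 (Data analysis), 4.6 and 6.3, replace the effectiveness of the training with *change in neck strength during the program*, and state that this change is not by itself evidence that training works. Optionally, as a sensitivity analysis, compare the observed change with that expected from the baseline strength-by-age relation, for example with age at visit in a mixed model. State the assumption that between- and within-subject age slopes agree, and do not present the result as removing confounding.

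3. Reconcile the Table 1 design summary, its Intervention row, footnote a and 4.5.2 on who trains and for how long.

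**Cost.** Wording, plus one optional analysis on data already planned. The downside is a weaker headline claim.

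Keeping goal 2 as written would need a concurrent or delayed-start comparison, which is a different study. For illustration only, assume individual 1:1 allocation, 11% risk without training, two-sided alpha 0.05, power 0.80 and no allowance for clustering. Then n per arm = (1.960√(2p̄q̄) + 0.842√(p₁q₁ + p₂q₂))²/(p₁ − p₂)², where q = 1 − p and p̄ is the mean of the two risks. Risk ratios of 0.5, 0.6, 0.7 and 0.8 need 784, 1300, 2442 and 5784 evaluable subjects in total, against the 1198 in 6.4. The protocol gives no training effect with which to choose among these.

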# 4.2 STUDY DESIGN AND METHODS-BRIEF

STUDY TYPE	Multicenter, observational, open analytical study
SAMPLE SIZE	1500
Sites	Sports facilities onsite at Gustavus Adolphus, member schools of the IMAC conference, and The Sanneh Foundation.
STUDY DURATION	Approximately 3 years
Study Arm(s)	Single-arm design

# Table 1: Study Design Summary

HSR# 17-4360

All subjects will undergo an instructor-led, standardized neckstrengthening training regime

#### **STUDY DESIGN** Subject recruitment and enrollment

Subjects (aged 5-22) involved in contact/collision sports programs will be recruited from and enrolled at schools and community-based sports facilities.

### Intervention

Subjects will be invited to participate in a twice-weekly, instructorled, neck-strengthening training program. In each training session, subjects will perform a variety of lightly-weighted and nonweighted resistance exercises.

#### Assessments and timeline

Demographic and sport history information will be collected at screening, and morphometric, cognitive, neck-strength, and eyetracking assessments will be made at baseline, and annually thereafter in the absence of a reported head injury. In addition, anthropometric and neck-strength measurements will be recorded immediately before and after training sessions at 6-month intervals to track improvements in neck strength. Subjects who experience concussion during the study will undergo assessments for eye-tracking and cognition at the time of the event; a subset of cognitive assessments will also be made on a daily basis following the event, until full recovery is achieved. If recovery is not achieved within a week, eye-tracking will be repeated. If symptoms continue to persist, additional cognitive assessments will be administered and repeated monthly until the subject fully recovers.

# Data analysis

Repeated-measures analysis of variance (ANOVA) will be used to evaluate the effectiveness of the training program for increasing neck strength. Relationships among neck-strength parameters and concussion risk and functional outcome measures will be evaluated via logistic and linear regression models. Analyses will be adjusted for sex to evaluate whether the results are independent of gender.

SCHEDULE

Week 1: Initial visit or call prior to enrollment to obtain informed consent; Baseline assessments made within 72 hours of enrollment Weeks 4 to 52: Assessments of neck strength made at 6-month intervals (+/- 3 days)a

Weeks 4 to 52: Assessments of concussion symptoms (if applicable) until symptoms resolve.

HSR# 17-4360

	
 
Time-of-event (within 1 day of event): Cognitive and eye-tracking assessments
 
Days 1-7 after event: Daily subset of cognitive assessments
 
Day 7: Eye-tracking assessment, neck-strength measurement
 
Weeks 4, 8, and 12 after event (+/- 3 days): Cognitive assessments
 

	a The neck-strengthening training regime will be administered for the length of the subject's sport program and during the period(s) of time corresponding to the subject's regular athletic training schedule.
BLINDING	This study is nonblinded.

# 4.3 STUDY OBJECTIVE

The primary objective of the study is to evaluate the impact of neck strength on the incidence and clinical outcomes of concussion among young athletes.

The study also generally aims to determine if implementation of a neck-strengthening program can significantly reduce the duration and severity of concussion symptoms in young athletes.

# 4.4 STUDY HYPOTHESES

The primary study hypothesis is that increased neck strength reduces in the incidence, severity, and duration of concussion symptoms.

# 4.5 STUDY ELIGIBILITY AND ENROLLMENT

#### 4.5.1 Study Population

Subjects will be youths aged 5 to 22 who are involved in one or more academic or community-based organized contact/collision athletic sports program(s). Approximately 1500 students will be recruited from Gustavus Adolphus College, member schools of the Independent Metro Athletic Conference (IMAC) conference, and The Sanneh Foundation, and enrolled in the study. The study population will be composed of players from multiple sports, and at a broad range of competitive levels. Study-site coordinators and/or trainers will be advised of the purpose and procedures of the study and will refer subjects to the Investigator for consideration. Subjects who meet all inclusion/exclusion criteria and have appropriate consent to participate in the study may be enrolled. The study is open to all races and both genders.

# 4.5.2 Duration of Investigation

Enrolled subjects may be followed for up to 3 years. The duration of training and assessment for subjects is anticipated to vary by sport and program. However, all subjects will HSR# 17-4360

complete the neck-strengthening training program twice weekly for the duration of time that they are enrolled in the study.

### 4.5.3 Informed Consent

Subjects enrolling in the study may not be capable of providing consent in which case consent will be obtained from the subject's parent/guardian/legal representative. Legal guardians will be provided with written consent forms detailing all risks, benefits and alternatives to subject participation.

For subjects aged 8 and above, written informed assent will be obtained from the subject. Informed consent will include a detailed description of the study, including its purpose, procedures, and risks.

The consent form will include information about the assessments conducted at baseline and at follow-up, and a description of the training regime. Research personnel from the Brain Injury Research Lab will prepare an informative video to be placed online, as well as verbally explain the information provided in the consent form and subjects and their representatives will be granted the opportunity to ask unlimited questions in English or any chosen language through the availability of a trained medical translation service.

The subject will be provided with a copy of the IRB-approved/stamped informed consent form. The Investigator or designee will ensure that all of the potential subject's questions and those of the subject's caregiver regarding study participation have been answered, and that the potential subject agrees to study participation. Written informed consent will then be obtained from the subject or the subject's legally authorized representative. A copy of the signed informed consent form shall be given to the subject/proxy, and the original stored on site at the Brain Injury Research Lab. The informed consent process shall be documented in the subject's records. No study-specific procedures will be conducted prior to obtaining consent.

#### 4.5.4 Subject Selection and Enrollment Procedures

Study site coordinators at each school or organization who are advised of the purpose and procedures of the study and will refer subjects to the Investigator for consideration. Once a subject has been identified, he/she will be approached by research personnel from the Brain Injury Research Lab or the study site coordinator and informed consent will be obtained prior to the screening process. Subjects will be considered enrolled in the study at the time the informed consent is obtained and when the subject ID has been assigned.

# 4.5.5 Inclusion Criteria/Exclusion Criteria

Youth athletes screened as potential study subjects must meet all of the following inclusion criteria and none of the following exclusion criteria.

# **INCLUSION CRITERIA:**

- 1. Involved in programmatic athletic activities with an ongoing duration of at least 4 weeks.
- 2. Written informed consent obtained by the subject or subject's legal guardian.
- 3. Written assent from subjects ages 8 years old and above
- 4. Subject is between the ages of 5 and 22 years, male or female.

#### HSR# 17-4360

5. Subjects from all racial and ethnic origins will have an opportunity to participate.

# **EXCLUSION CRITERIA:**

1. Corrected vision less than 20/500.

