#### 4.6 STUDY TREATMENT

Subjects will engage in an instructor-led, supervised, manual-resistance training program twice weekly. At each session, subjects will perform a variety of nonweighted resistance exercises, previously shown in a clinical trial to be safe and effective for use in pediatric populations (ClinicalTrials.gov identifier, NCT02455037) and lightly weighted exercises using barbells, and commercial neck strengthening equipment (eg, NekkDekk and/or IronNeck).

The effectiveness of the strength training regime over time will be assessed by measuring neck girth and neck strength at the beginning and end of training sessions at 6-month intervals, for as long as the subject continues the sport program or until he/she leaves the study.

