# Neck Strength Parameters

HSR# 17-4360

Neck strength (extension, flexion, left and right lateral measurements) will be assessed using a hand-held commercial dynamometer that is effective for measuring neck strength. Subjects will be permitted to rest between measurements to minimize risk of injury.

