# 4.8 STUDY TIMELINE

# 4.8.1 Screening/Baseline:

Once a potential study subject is identified, informed consent will be obtained. After this, patients will be asked or undergo

• General medical questions to affirm inclusion/exclusion criteria

*If they are eligible for enrollment, they will then undergo:* 

- Training on all aspects and requirements of the study, including the neck-strengthening training program, concussion and adverse event reporting, and frequency and expectations for follow-up measurements of neck strength
- Morphometric assessments
- Cognitive evaluations
- Eye-tracking algorithm
- Neck-strength assessment

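### No entry criterion concerns the neck, so as written an athlete with a current neck injury qualifies for neck strength testing and neck resistance training

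*Protocol*

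**What the plan says.** Section 4.5.5 of the protocol states that screened athletes "must meet all of the following inclusion criteria and none of the following exclusion criteria". The exclusion list has a single entry: "Corrected vision less than 20/500". The inclusion entries cover sports participation ("Involved in programmatic athletic activities with an ongoing duration of at least 4 weeks"), consent, assent, age, and openness to all racial and ethnic groups.

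At screening, section 4.8.1 lists "General medical questions to affirm inclusion/exclusion criteria". Those found eligible go on to study training and to the morphometric, cognitive, eye-tracking and neck-strength assessments.

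Section 4.7 measures neck strength in extension, flexion and both lateral directions with a hand-held dynamometer, and adds: "Subjects will be permitted to rest between measurements to minimize risk of injury". Section 4.6 describes a supervised manual-resistance program that also includes "lightly weighted exercises using barbells, and commercial neck strengthening equipment". Section 4.5.2 says that all subjects will "complete the neck-strengthening training program twice weekly for the duration of time that they are enrolled in the study". Section 6.1 evaluates the safety of the program by the injuries and other adverse events related to it.

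Table 1 in section 4.2 gives a "Single-arm design". Section 6.3 judges the training effect on neck strength by repeated-measures analysis of variance.

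**The concern.** The intervention and the main exposure measurement both load the neck, yet eligibility is silent about it. The one exclusion, on vision, appears to serve the eye-tracking measurement and does nothing for the safety of the neck training. The population is contact and collision athletes aged 5 to 22, many of them minors.

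Three things are at stake, in this order:

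- **Safety.** The subjects plausibly most exposed to harm from neck loading are not identified at entry.
- **Measurement.** A baseline strength lowered by pain or injury is a poor value of the exposure in goal 1 (section 4.1). It also enters the change from baseline, where no control arm helps to interpret it.
- **Attribution.** Neck symptoms are not among the listed baseline assessments, so there is no stated reference against which to judge a neck complaint that appears during training.

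**Working it through.** The protocol states no figure on this point, so there is none to reproduce. The check is a reading of the sections against each other, followed by an illustration of size.

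**1. Is the list closed?** Yes. Section 4.5.5 requires every listed inclusion and no listed exclusion. None of the entries mentions the neck, freedom from injury, or clearance to train. Taking part in a sports program is not the same as being uninjured.

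**2. Does screening add a ground for keeping someone out?** No. Section 4.8.1 ties the medical questions to the listed criteria, and the only medical criterion listed is vision.

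**3. What follows eligibility?** Four-direction strength testing at baseline (4.7, 4.8.1) and resistance training twice a week (4.5.2, 4.6).

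**4. Does the protocol see a risk?** Yes. Section 4.7 allows rest in order to limit injury during testing, and section 6.1 plans for training-related injuries. In section 4.6 the statement of earlier safety evidence is attached to the nonweighted exercises. Nothing says that this evidence covers people who start with a neck injury.

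**5. Could a statistical analysis plan repair it?** No. Entry criteria are set in the protocol.

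**6. How large could the effect on mean change be?** Inputs, all assumed because the protocol gives none:

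- p0 = share of subjects with a current neck injury at baseline
- p1 = the same share at follow-up
- d = proportional loss of strength while injured
- healthy mean strength = 100, and no training effect

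Baseline mean = 100(1 − p0·d). Follow-up mean = 100(1 − p1·d). Spurious change = 100·d·(p0 − p1) points, or d(p0 − p1)/(1 − p0·d) as a fraction of the baseline mean.

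| p0 | p1 | d | Change, points | Change, % of baseline mean |
|---|---|---|---|---|
| 1% | 0 | 10% | +0.1 | 0.1/99.9 = +0.1% |
| 3% | 0 | 30% | +0.9 | 0.9/99.1 = +0.9% |
| 5% | 0 | 20% | +1.0 | 1.0/99.0 = +1.0% |
| 10% | 0 | 30% | +3.0 | 3.0/97.0 = +3.1% |
| 3% | 3% | 30% | 0 | 0 |
| 3% | 5% | 30% | −0.6 | −0.6/99.1 = −0.6% |
| 0 (screened out) | 3% | 30% | −0.9 | −0.9/100 = −0.9% |

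The first four rows assume full recovery and no new neck injury. The next two show that the shift vanishes when injury is equally common at both times and turns negative when it is commoner later. The last row shows that screening at baseline alone, with nothing done at follow-up, would itself push the measured gain downward.

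**The case against.** The strongest reply is that the protocol has other safeguards. Coordinators refer athletes to the investigator for consideration, and those who qualify may be enrolled, which is permission and not an obligation (4.5.1, 4.5.4). Training is offered by invitation (4.2), sessions are supervised (4.6), and precautions and risks are reviewed with each subject (5.1). These lower the risk, and they mean that no injured athlete is bound to be enrolled. But none is an entry criterion, none tells the investigator to ask about the neck, and none protects the baseline strength value. The gap therefore stands.

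Two stronger readings are tempting, and the protocol supports neither.

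- *Recovery from injury will pass as a training gain.* A reader might infer this from the single-arm design. It holds only if injured entrants recover and few others are injured by follow-up. Subjects play contact sport throughout and are measured every 6 months, so new injuries lower later values too. Nothing in the protocol selects injured athletes at entry.
- *A neck complaint during training cannot be told apart from one present at entry.* Section 4.9 has onset (where applicable), maximum intensity, frequency and attribution recorded for each adverse event. It opens a new record when an event worsens. Section 6.1 adds follow-up with the subject, trainer or guardian. The missing baseline record makes attribution harder, not impossible.

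It is also fair to say that the lack of a control arm, in growing subjects followed for up to 3 years, matters more for reading strength gains than this point does.

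**Conclusion.** The gap is real and rests on the protocol's wording alone: an athlete with a current neck injury meets the criteria for neck testing and neck training, while the protocol acknowledges injury risk from both. It is chiefly a safety matter, and that part does not depend on any average or assumed figure.

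The statistical consequence is secondary. An injury-lowered baseline is a mismeasured goal 1 exposure and can distort the mean change. Under assumed shares of 1% to 10% and deficits of 10% to 30%, the shift is at most about 3.1% of mean baseline strength when no one is injured at follow-up. It is zero or negative when injury is as common or commoner then. Its size and net direction are therefore not known. A claim that the gap inflates the training effect would go beyond the documents. The change is worth making because it is cheap and protects subjects, not because the analysis would otherwise fail.

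**What to change.** Reconcile section 4.5.5 with sections 4.6, 4.7 and 6.1:

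1. Add to 4.5.5 an entry criterion, or a deferral of the baseline assessment, for current neck injury or neck symptoms. What counts, and for how long, is a clinical matter for the investigator to define.
2. Add the matching question to the screening questions in 4.8.1 and record the answer, so that a baseline reference exists for later neck complaints.
3. Ask and record the same question at the 6-month strength assessments in 4.8.2, so that the analysis of change can treat baseline and follow-up alike. Without this step, the new criterion alone would tilt the measured gain downward, as the last row of the table shows.

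The cost is one criterion and one question per strength visit. A few athletes will be excluded or will enter later.
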